Only certain SLE subgroups or organ systems may respond to a particular agent, an important consideration for early phase trials. Concurrent use of immunosuppressive medications, like mycophenolate mofetil, azathioprine, methotrexate and corticosteroids, creates further biologic variability in an already heterogenous disease and confounds the interpretation of data in human studies, since these medications might interfere with or confound the mechanism of the agent(s) studied. This practice also increases the response in the comparator arms, limiting the possible differences between treatment and placebo in SLE clinical trials, necessitating the prolonged study of larger patient numbers for adequate power, and further compromising the clinical interpretability of results. Withdrawal of background immune suppression has been considered as an option to limit study time and patient exposures to untested therapies, but the community has been concerned about its safety. The BOLD (Biomarkers of Lupus Disease) trial, in which a brief course of parenteral steroids is utilized to induce a state of remission or low disease activity while background medications are withdrawn, has shown evidence this approach is safe and effective (11). Time to first flare averaged 72 days (CI 43–91), with 100% of the patients flaring by 24 weeks.

In the BLISS trials of belimumab in SLE the systemic response index (SRI), a composite measure of disease activity, was used as the primary endpoint. SRI is a landmark index defined as the composite of ≥ 4 point reduction in total SLEDAI score, with no new BILAG A or no more than one new BILAG B domain score and no more than 10% worsening in physician's global assessment (PGA), compared to baseline. Another composite measure, the SRI-BILAG (BICLA) has been used in the EMBLEM phase II trial of epratuzumab in SLE. BICLA requires the achievement of BILAG-2004 improvement (BILAG A to B/C/D, BILAG B to C/D, and no BILAG worsening), along with no deterioration in SLEDAI total score and no more than 10% worsening in PGA. In the BOLD study, BICLA was found to be more sensitive to change than SRI, when anchored to the simpler BOLD improvement criteria (drop of \geq one BILAG grade or ≥ 4 SLEDAI points) anchored to the clinician's determination of significant clinical improvement (11).

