This is a prospective placebo-controlled randomized study. Patients will enter with active disease. After informed consent and screening procedures are completed, enrolled patients may be optionally treated with intramuscular methylprednisolone acetate and background immune-suppressive medications will be withdrawn. Injection of methylprednisolone acetate may be repeated in week 2 at the discretion of the investigator, to induce a state of remission/low disease activity. Patients will be assigned to begin the study medication upon enrollment (baseline, week 0). Patients will be randomized 1:1 to Aggrenox or half of an 81mg aspirin tablet twice daily for 24 weeks. Aggrenox will be initiated at a single bedtime dose for a week, followed by twice daily administration for the rest of the study, to minimize the risk of side effects (e.g. dizziness, headache). Aspirin will be titrated similarly to preserve blinding. Gelatin capsules will be used to cover the pills in order to preserve the blinding.

Participants will be evaluated at baseline (week 0), week 2, week 4 and every 4 weeks until the completion of the study at week 24. An additional study visit may be scheduled at the time of a clinically significant flare (flare visit). Evaluation of general health status, adverse events and lupus disease activity (SLEDAI, BILAG, PGA, CLASI, DIAL, SF-36v2, Lupus QoL, FACIT-fatigue, PSQI, CES-D) will be performed at baseline, week 4 and every subsequent visit. Time to first flare and severity of first flare will be examined. At the time of a clinically significant flare

(defined as at least one BILAG letter grade increase or an increase of ≥ 3 points in SLEDAI AND clinician determination of clinically significant deterioration) patients may elect further treatment with intramuscular methylprednisolone acetate or, if necessary DMARD therapy, but will continue the study as permanent nonresponders.

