Patients will have CBC with differential, metabolic profile, urinalysis, anti-dsDNA, and complement studies performed at baseline, each of the subsequent monthly visits through week 24 and the flare visit. If urine dipstick is $\geq 2+$, a protein/creatinine ratio will be performed at the following visit (or sooner at the discretion of the investigator). Pharmacodynamic and exploratory blood and urine biomarker samples will be drawn prior to first dose at baseline, at weeks 8 or 12, week 24 and at the flare visit. Some of the stimulated cell gene expression and signaling pathway work will be performed on deidentified samples in collaboration with Drs. [name] and [name] at Beth Israel Medical Center in Boston Massachusetts. We will have a material transfer agreement with that institution. In the context of our ancillary study of heart rate variability in lupus, a 5-minute ECG will be performed at each monthly visit and at the flare visit (please see attached protocol).

Summary of Medications and Medication Changes

At screening, participants may be receiving daily prednisone at a dose of 20mg or less, and/or one or more of the following DMARDs: hydroxychloroquine, methotrexate, azathioprine and mycophenolate mofetil, and must be agreeable to discontinue their background immune suppressants upon enrollment. Patients taking hydroxychloroquine upon enrollment will however continue the medication throughout the study.

All participants may be administered optional intramuscular methylprednisolone acetate upon enrollment (usually 160mg, but dose may adjusted based on clinical judgment). Intramuscular steroid treatment may be repeated at weeks 2 at the discretion of the investigator, to induce a state of remission/low disease activity while background medications are withdrawn. Patients on oral steroids will be given an optional rapid taper over 3-4 weeks.

Duration of participation

Participants will receive treatment for a total of 24 weeks.

Patient enrollment

A maximum of 50 patients meeting the inclusion criteria and not meeting the exclusion criteria will be enrolled in the study. The enrollment period is expected to last for at least 18 months but could last as long as four years.

Data collection and analysis

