Data will be collected by study personnel who will be kept blinded to treatment assignments. A trained study coordinator will provide data monitoring and quality assurance checks on the database. The final data will be pooled and analyzed by the investigators.

E. Statistical methods

The primary analysis will be an intention-to-treat two by two table.

Primary endpoint: A two by two table analysis of rate of response by the BICLA response index at week 24 compared to baseline (week 0) in patients on aspirin versus Aggrenox regimens, with non-response attributed to patients who receive defined non-responder treatments and/or withdraw early. Please see below for power calculations based on expected response rates. Independent predictors of BICLA response, including baseline biomarkers, biomarker responses to Aggrenox treatment, demographics and amount of steroids administered, will be further investigated by exploratory logistic regression modeling.

Secondary endpoints: Flare rates at week 24 compared between completers among treatment groups. Time to flare (log rank test). SRI 4/5 at week 24, BICLA and SRI 4/5 at each month. HRQOL comparing treatment groups versus baseline at week 24 and at each month. Although our primary endpoint is based on the BICLA response, an accepted outcome for lupus clinical trials which serves as a pilot response indicator for future trials, it is likely that some secondary endpoints, such as time to flare will be more sensitive, and more likely to achieve significance in a pilot study.

Exploratory endpoints: SRI component analyses and CLASI responses. Refinement in BICLA and SRI analysis using a propensity score derived by multiple potential confounders identified in exploratory single variate analysis. Relation of clinical and biologic endpoints with heart rate variability measures by multivariate analysis.

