An absolute difference of ≥ 12 to 15% in the response rate is however considered clinically significant in other lupus trials. Since this is a pilot study, a clinically significant (12% or greater absolute difference), but not statistically significant difference, might be considered justification for a larger study. Even if this pilot study does not reach statistical significance, the proposed exploratory biomarker studies evaluating T and B cell phenotypes, T/B cell functional studies, gene expression or serum cytokine/chemokine profiles might be used to refine the entry criteria and biologic treatment goals for a further study and/or underscore the rationale for an expansion of this study for more power of discrimination. Finally, the BICLA and other flare analyses will be performed at each monthly visit, increasing the likelihood of finding differences, should they exist, when including these secondary analyses.

An interim analysis will be performed after 20 patients will have completed the study, and will be used to assess the quality of the data collected and the treatment effects. Consideration of sample size changes can be discussed at that time.

F. Gender/Minority/Pediatric Inclusion for Research

Participants will be age 18 or older. Race, minority status and gender will not affect enrollment.

G. Human participants

The study population will include male/female patients with SLE, of age 18 or older and of all races.

Inclusion Criteria:

1. Patients with SLE meeting the ACR Classification Criteria (19)
2. Males or females, age 18-70
3. Evidence of positive ANA or anti-dsDNA within one year of screening
4. SLEDAI ≥ 4 or ≥ 1 BILAG B or A at screening, despite standard of care

Exclusion Criteria

1. WBC $< 2,000/\text{mm}^3$, lymphocytes $< 300/\text{mm}^3$ (last known labs)
2. AST or ALT > 3 times above normal cut off values (last known labs)
3. Acute lupus nephritis defined as class II, III, IV or V nephritis diagnosed within 6 months or prot/creat > 1.5 gm/gm due to active lupus or in process of receiving induction therapy for nephritis
4. Active CNS lupus affecting mental status
5. Pregnancy or breast feeding
6. Current requirement for anticoagulation
7. Contraindication to aspirin or dipyridamole, including history of recent or severe GI bleeding, hemoglobin < 9 mg/dL, platelet count of $< 30,000/\text{mm}^3$ or unstable platelet count (last known labs)

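### SRI-4 and SRI-5 are compared with no minimum week-0 SLEDAI, so patients who cannot reach them may be counted in both arms and dilute the difference

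*Combined protocol and SAP*

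**What the plan says.** - **Entry** (section G, inclusion criterion 4): "SLEDAI ≥ 4 or ≥ 1 BILAG B or A at screening, despite standard of care". The two routes are joined by an or. The BILAG route carries no SLEDAI minimum, and the criterion is checked at screening.
- **The index** (section C, Preliminary studies): "SRI is a landmark index defined as the composite of ≥ 4 point reduction in total SLEDAI score", together with limits on new BILAG grades and "no more than 10% worsening in physician's global assessment (PGA), compared to baseline". SRI-5 is not defined anywhere.
- **The analysis** (section E, Secondary endpoints): "SRI 4/5 at week 24, BICLA and SRI 4/5 at each month". No analysis set for the SRI, minimum week-0 SLEDAI or stratification by week-0 SLEDAI is given. Section E takes baseline as week 0.
- **Power** (section E, Power/Sample size calculation): the rates and the table are for BICLA. No SRI response rate or SRI power is stated.

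**The concern.** A patient's SLEDAI can fall by no more than its starting value. An index that demands a fall of a fixed size is therefore closed to anyone who starts below that size, whatever the treatment does. Inclusion criterion 4 lets such patients in through the BILAG route. Because it applies at screening while response is counted from week 0, even the SLEDAI route does not guarantee a week-0 score of 4.

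If these patients sit in the SRI denominators, both arms carry non-responses that say nothing about dipyridamole. The estimated SRI difference is then smaller than the difference among patients in whom the index can work. Because attainability is fixed at week 0, the same patients weigh on the week-24 comparison and on every monthly one.

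**Working it through.** **1. Who can reach the index.** SLEDAI is taken as a score with a floor of 0, so the largest possible fall equals the week-0 score. SRI-5 is read by its name as a fall of at least 5 points.

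| Week-0 SLEDAI | SRI-4 | SRI-5 |
|---|---|---|
| 0 to 3 | impossible | impossible |
| exactly 4 | possible (fall to 0) | impossible |
| 5 or more | possible | possible |

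Every row is open to a patient who entered with a BILAG A or B. A BILAG-route patient with SLEDAI of 5 or more can reach both indices, so the entry route alone does not decide attainability. The share unable to respond is at least as large for SRI-5 as for SRI-4.

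**2. Inputs for size.** Allocation: "Patients will be randomized 1:1 to Aggrenox or half of an 81mg aspirin tablet twice daily for 24 weeks". Size: "A maximum of 50 patients meeting the inclusion criteria and not meeting the exclusion criteria will be enrolled in the study", so 25 per arm. Alpha is 0.05 (power table; sidedness is not stated, and two-sided reproduces the table). The documents do not give f, the share of patients unable to respond; 20% and 40% are used as assumptions. They give no SRI response rates either, so the BICLA pair 40% v 5% from the power table is borrowed as the assumed SRI rates among patients able to respond.

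**3. The plan's own figures.** Pooled two-proportion formula, two-sided, no continuity correction, with p̄ = (p1 + p2)/2:

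Power = Φ{ [ |p1 - p2| - 1.96 √(2p̄(1 - p̄)/n) ] / √[(p1(1 - p1) + p2(1 - p2))/n] }

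| Pair | 60/20 | 55/15 | 50/10 | 45/10 | 40/5 | 35/5 | 35/3 |
|---|---|---|---|---|---|---|---|
| Plan | 0.84 | 0.86 | 0.89 | 0.80 | 0.86 | 0.77 | 0.84 |
| Formula | 0.845 | 0.866 | 0.895 | 0.811 | 0.865 | 0.772 | 0.844 |

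The table reproduces to about 0.01. It concerns BICLA and is not affected by this point.

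**4. Dilution.** With a share f unable to respond in each arm, the observed rates are (1 - f)p1 and (1 - f)p2, so the observed difference is (1 - f)(p1 - p2).

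- f = 20%: 0.8 × 40% = 32% and 0.8 × 5% = 4%; difference 28 points instead of 35.
- f = 40%: 0.6 × 40% = 24% and 0.6 × 5% = 3%; difference 21 points.

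**5. Power, same formula.**

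- f = 20%, all 25 per arm (32% v 4%): (0.28 - 0.213)/0.101 = 0.66, power 0.746.
- f = 20%, restricted, 0.8 × 25 = 20 per arm (40% v 5%): (0.35 - 0.259)/0.120 = 0.76, power 0.777.
- f = 40%, all 25 per arm (24% v 3%): (0.21 - 0.189)/0.092 = 0.22, power 0.588.
- f = 40%, restricted, 0.6 × 25 = 15 per arm (40% v 5%): (0.35 - 0.299)/0.138 = 0.37, power 0.644.

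**6. Sensitivity.** At 60% v 20%, the all-patient and restricted powers are 0.690 and 0.752 (f = 20%), and 0.511 and 0.619 (f = 40%). The gain also depends on the test. At 40% v 5% and f = 20%, exact calculation gives 0.81 v 0.82 for the uncorrected chi-square and 0.67 v 0.72 for Fisher's test. Across the pairs and tests examined, the gain at f = 20% is about 1 to 7 points.

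**The case against.** The strongest case for leaving the plan alone has four parts.

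- **No validity error.** Under 1:1 randomisation the patients unable to respond are expected equally in both arms. The false-positive risk is not raised and the dilution is conservative. This stands, apart from chance imbalance at 25 per arm. Counting everyone also answers a legitimate question and fits the primary approach ("The primary analysis will be an intention-to-treat two by two table"), which is why the all-randomised result should be kept.
- **Unknown size.** No baseline SLEDAI distribution is given, so f could be near zero, and the illustrative rates are BICLA rates. This stands: the arithmetic shows what f would do, not what f is.
- **Little power recovered.** Most of the loss comes from having fewer informative patients, which restriction cannot undo. This stands. What restriction does restore is the size of the difference.
- **Peripheral endpoints.** Only secondary comparisons in the randomised part of a pilot are affected, and section E expects time to flare to be more sensitive. This stands. The exploratory SRI component analyses would let the SLEDAI component be inspected, but neither they nor the propensity-score refinement take these patients out of the SRI comparison.

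A reader might infer two stronger points that the documents do not support. The first is that a patient at SLEDAI of exactly 4 is shut out of both indices; a fall to 0 meets "≥ 4 point reduction in total SLEDAI score", so only SRI-5 is closed. The second is that dilution endangers the 12% absolute difference that section E says might justify a larger study. That criterion follows the BICLA power table and is not tied to the SRI, and the diluted differences above (28 and 21 points) still exceed it. It forms no part of this point.

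**Conclusion.** The point holds as a gap in the definition of the secondary SRI analyses. Eligibility allows patients with week-0 SLEDAI of 0 to 3, who cannot reach SRI-4 or SRI-5, and patients at exactly 4, who cannot reach SRI-5. Nothing in section E removes or separates them. The SRI difference is multiplied by (1 - f) at every visit. On the borrowed 40% v 5%, the loss is 7 points at f = 20% and 14 points at f = 40%; restriction restores the 35-point difference but adds only about 3 and 6 points of power. These figures rest on an assumed f, on BICLA rates standing in for SRI rates, and on SRI-5 meaning a fall of at least 5 points. The primary BICLA analysis and its power table are untouched by this point, and the open-label group B of the 2015 amendment has no control arm to compare.

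**What to change.** Add to section E, under Secondary endpoints, text to this effect:

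> SRI-5 is defined as SRI with a fall of at least 5 SLEDAI points. SRI-4 is analysed in randomised patients with a week-0 SLEDAI of 4 or more, and SRI-5 in those with a week-0 SLEDAI of 5 or more, using the score taken before the first dose. Patients are analysed by assigned arm, with the non-responder rules of the primary endpoint. The number excluded is reported for each arm. The all-randomised result is shown as supportive.

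The subset is fixed by a pre-dose value, so the randomised comparison is kept. SLEDAI is already scored at week 0, so no new data are needed and the entry criteria stay as they are. The cost is smaller SRI denominators that differ from each other and from the BICLA denominator, which makes side-by-side reading of the three indices less direct. The supportive all-randomised result limits that cost.

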RESEARCH PROTOCOL

Title of project: Dipyridamole Assessment for Flare REduction in SLE: The DARE study

Principal Investigator: [name]

Co-Investigator: [name]

Co-Investigator: [name], PhD

Co-Investigator: [name]

Co-Investigator: [name]

Co-Investigator: [name], PA-C

Consultant: [name].

Abstract

T cells in systemic lupus erythematosus (SLE) express an abnormal phenotype characterized by increased effector functions and deficient regulatory responses. Dipyridamole, a phosphodiesterase inhibitor extensively used in combination with low dose aspirin in secondary stroke prevention, has been proposed as a specific T cell directed treatment for SLE. Dipyridamole inhibits the calcium/calcineurin/NF-AT pathway in SLE T cells *in vitro* and abrogates expression of cytokines and costimulatory molecules, eventually also affecting B cell responses. Dipyridamole delays the emergence of lupus related pathology in lupus prone mice, but has not yet been studied in humans with SLE. We aim to investigate the efficacy of dipyridamole in the prevention of flares in SLE patients after withdrawal of background immunosuppressive medications. We will additionally evaluate the safety and tolerability of dipyridamole and its impact on quality of life measures in this population. Furthermore, the effect of dipyridamole on T and B cell biomarkers will be examined.

A. Specific aims

Primary objective: To examine the efficacy of dipyridamole/aspirin (Aggrenox, Boehringer Ingelheim Pharmaceuticals, Inc.) for flare prevention in patients with SLE as measured by the BICLA endpoint (improvement in disease activity compared to baseline without new flare or additional treatments).

Secondary objectives: To examine the effect of dipyridamole on:

1. Flare rate and time to first flare
2. Systemic response index (SRI) 4/5 at week 24, BICLA and SRI 4/5 at each month, SRI component analyses, CLASI and DIAL responses

3. Patient reported outcomes, including: health related quality of life (measured by the Lupus QoL, LupusPRO and the Short Form 36v2), fatigue (measured by the FACIT-fatigue score), sleep quality (measured by the Pittsburgh Sleep Quality Index (PSQI)) and depression (measured by the Center for Epidemiologic Studies Depression (CES-D) Scale)
4. Tolerability and safety

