Biologic Endpoints: Changes in B cell and T cell subsets, relevant gene expression patterns, B-T cytokine profiles and cell-bound complement split products and urinary biomarkers at baseline versus week 24 in each treatment group. Evaluation of B Cell/T cell expression patterns in patients with higher versus lower IL6, IL17 and IL23 expression detected at baseline. These endpoints will be evaluated both as changes with Aggrenox versus aspirin treatment (non parametric analysis) and as components of multivariate modeling and propensity score analysis as described above. An exploratory responder analysis will also be performed (changes in these biomarkers with response versus non-response in patients receiving Aggrenox). The latter analysis may need to be observational only, as it is likely to be underpowered and diluted by patients who may not have begun the trial with the characteristic abnormalities in T cell subset activity.

Power/Sample size calculation

We base this calculation on preliminary data from the BOLD study (11) which is an exploration of underlying biology in patients with SLE who receive steroids and are withdrawn from background treatments, in other words identical to the aspirin group in the current proposal. To date we have analyzed data from 31 patients who completed the BOLD protocol and these outcomes suggest that no more than 20% of the aspirin group will achieve a BICLA response at week 16 (range 1-20%) and no more than 5% achieves a BICLA response at week 24 (range 0-10%). Assuming a 35 to 50% response rate in the Aggrenox group at week 24, a sample size of 50 patients will provide a power around 80% at a significance level of 0.05 at week 24. By these settings and assumptions, the following power estimates are obtained.

Power calculations for a 50 patient study, if alpha=0.05 with response rates:

	Rate 1	Rate 2	Rate 3	Rate 4	Rate 5	Rate 6	Rate 7
Aggrenox n=25	60%	55%	50%	45%	40%	35%	35%
Aspirin n=25	20%	15%	10%	10%	5%	5%	3%
power	0.84	0.86	0.89	0.80	0.86	0.77	0.84

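### The quality-of-life analysis names no model and does not use the baseline score as a covariate; its wording leaves the contrast between arms open to two readings

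*Combined protocol and SAP*

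**What the plan says.** Section A (Specific aims) makes patient-reported outcomes the third secondary objective. They begin with "health related quality of life (measured by the Lupus QoL, LupusPRO and the Short Form 36v2", followed by fatigue, sleep quality and depression scales.

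Section D (Research design and Methods) lists SF-36v2, Lupus QoL, FACIT-fatigue, PSQI and CES-D among the assessments and says that evaluation "will be performed at baseline, week 4 and every subsequent visit". LupusPRO is not in that list. On allocation, the section says: "Patients will be randomized 1:1 to Aggrenox or half of an 81mg aspirin tablet twice daily for 24 weeks".

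Section E (Statistical methods), under secondary endpoints, gives the analysis in one sentence: "HRQOL comparing treatment groups versus baseline at week 24 and at each month". It names no test, model, covariate or effect measure, and no other section supplies one. The adjustments planned for clinical outcomes in section E are exploratory: logistic modelling of BICLA response, and a propensity-score refinement of BICLA and SRI. Quality of life is not named in either.

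**The concern.** Two problems follow from the sentence, depending on how it is read.

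- **Change from baseline, compared between arms.** Randomization makes this valid. But subtracting the whole baseline score over-corrects whenever the correlation between baseline and follow-up is below 1. The result is noisier than a baseline-adjusted comparison and reacts more to chance imbalance at baseline.
- **Each arm tested against its own baseline.** This does not estimate a drug effect. Section D lets patients in both arms receive intramuscular steroid and has both arms stop background immunosuppressants, so either arm can move for reasons unrelated to dipyridamole. Finding one arm significant and the other not is not evidence of a difference between them.

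At stake is how much a small trial can learn about its patient-reported objectives. Enrollment is capped ("A maximum of 50 patients meeting the inclusion criteria and not meeting the exclusion criteria will be enrolled in the study"), so precision cannot easily be gained through numbers. Section E itself expects some secondary endpoints to be more sensitive than the primary.

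**Working it through.** **The plan's own figures.** The documents give no power, SD, correlation or effect size for quality of life. The only power figures are for BICLA: "Power calculations for a 50 patient study, if alpha=0.05 with response rates". They reproduce with a two-sided pooled normal approximation, power = Φ((d − 1.96·se₀)/se₁), with 25 per arm. For 60% against 20%: se₀ = √(0.4·0.6·2/25) = 0.1386, se₁ = √((0.24 + 0.16)/25) = 0.1265, and power = Φ((0.40 − 0.2716)/0.1265) = 0.845.

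The seven results are 0.845, 0.866, 0.895, 0.811, 0.865, 0.772 and 0.844, against the stated 0.84, 0.86, 0.89, 0.80, 0.86, 0.77 and 0.84. This confirms 25 per arm and two-sided 0.05 as the working basis. It says nothing about quality of life.

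**Inputs.**
- From the documents: 25 per arm (power table), alpha 0.05 (power table), 1:1 allocation (section D).
- Assumed: equal SD at baseline and week 24; baseline to week-24 correlation r from 0.3 to 0.8; a true between-arm difference of 0.5 SD.

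**Reading 1: change score between arms.** In units of the outcome variance, the residual variance is
- change score: 2(1 − r)
- ANCOVA: 1 − r²
- ratio, ANCOVA to change: (1 − r²)/(2(1 − r)) = (1 + r)/2, below 1 for every r below 1.

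The number per arm that change scores need to match ANCOVA with 25 is 25/((1 + r)/2). Power is Φ(0.5/√(2v/25) − 1.96), with v the residual variance. The small cost of one degree of freedom for the covariate is ignored.

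| r | change v | ANCOVA v | ratio | n per arm to match | power, change | power, ANCOVA |
|---|---|---|---|---|---|---|
| 0.3 | 1.40 | 0.91 | 0.65 | 38.5 | 0.32 | 0.46 |
| 0.5 | 1.00 | 0.75 | 0.75 | 33.3 | 0.42 | 0.53 |
| 0.7 | 0.60 | 0.51 | 0.85 | 29.4 | 0.63 | 0.70 |
| 0.8 | 0.40 | 0.36 | 0.90 | 27.8 | 0.80 | 0.84 |

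For r = 0.5: change score 0.5/√(2·1.00/25) = 1.768, and Φ(1.768 − 1.96) = 0.42; ANCOVA 0.5/√(2·0.75/25) = 2.041, and Φ(2.041 − 1.96) = 0.53.

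**Reading 2: each arm against its own baseline.** Suppose there is no true difference and both arms improve by m SD (assumed). The within-arm standard error is √(2(1 − r)/25). The chance p that one arm reaches significance is Φ(m/se − 1.96) + Φ(−m/se − 1.96), and the chance that exactly one of the two does is 2p(1 − p). For r = 0.5 and m = 0.3: se = 0.20, p = 0.323, and 2·0.323·0.677 = 0.44. Over m = 0.2 to 0.5 and r = 0.3 to 0.7 the result runs from 0.18 to 0.50. A misleading split between arms would therefore be common.

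**The case against.** The strongest reply is that the plan does intend a between-arm comparison. The sentence speaks of comparing treatment groups, and the primary endpoint in the same section has the same form: response relative to week 0, aspirin against Aggrenox. A reader might infer that quality of life is tested within arms instead of between them. The documents do not support that. The between-arm reading is the more natural one, and the within-arm reading is only left open. This part of the reply stands, so the defect is unspecified and ambiguous wording, not a stated wrong choice.

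The size of the gain also cannot be fixed from the documents. At r = 0.8 the power gap is 0.80 against 0.84, which is small. At r = 0.5 and 0.5 SD, neither analysis reaches conventional power. This stands too, and it is why the result is given as a range.

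A reader might extend the point to the biologic endpoints, where the plan sets out "cell-bound complement split products and urinary biomarkers at baseline versus week 24 in each treatment group". That does not follow. The same paragraph goes on to plan a non-parametric comparison of changes between Aggrenox and aspirin, so a between-arm contrast is already stated there.

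Nor can it be said that every instrument has a scheduled baseline, because LupusPRO is missing from the section D list.

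Finally, this is one secondary endpoint in a self-described pilot that makes no power claim for it. That limits the weight of the point. It does not remove the gap, because no section says how the patient-reported scores will be modelled.

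**Conclusion.** The point holds as a gap in specification with a moderate cost. Under the natural reading the planned comparison is valid but gives up precision: ANCOVA variance is 0.65 to 0.90 of the change-score variance for correlations of 0.3 to 0.8, or 28 to 39 patients per arm (rounded up) to match ANCOVA with 25. These figures assume equal variances and full enrollment of 25 per arm. The power figures also assume a 0.5 SD difference. The direction does not depend on the correlation chosen; the size does. Under the less likely reading there would be no treatment-effect estimate at all, which is reason enough to remove the ambiguity.

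The primary BICLA analysis is unaffected. The point concerns only the randomized comparison (group A). The January 2015 amendment's open-label group B has no control arm, so no between-arm model applies to it.

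**What to change.** For randomized group A, replace the quality-of-life sentence in section E with:

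> Between-arm difference in score at week 24 from a repeated-measures model (or ANCOVA) with treatment, visit, treatment by visit and baseline score; monthly estimates with 95% intervals from the same model.

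If ANCOVA is chosen, it is fitted at a single visit and the visit terms drop out. Apply the analysis to SF-36v2, Lupus QoL, FACIT-fatigue, PSQI and CES-D, all of which have a scheduled baseline. Name the fatigue, sleep and depression scales explicitly, since the present sentence mentions only quality of life. Include LupusPRO if its baseline is collected, and reconcile its absence from the section D list with the objective in section A.

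The cost is analysis wording only. No new data are needed for the five listed instruments, and the sample size and primary analysis do not change.
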